1.0 Introduction

Colorectal cancer (CRC) is the third most common cancer diagnosis and age-standardized source of cancer mortality in Europe (GLOBOCAN 2012). Up to one quarter of CRC patients have liver metastases at the time of diagnosis, and 50% will develop liver metastasis within five years (Aliberti 2011); of patients who develop metastatic disease, 40% will have metastases confined exclusively to the liver (Benson 2007). Fewer than 25% of patients with metastatic CRC (mCRC) are eligible for surgical resection or ablative therapies, and of those who are, 70% recur within 3 years (Pwint 2010). With the burden of CRC on the rise – estimated incidence in Europe increased by nearly 20,000 cases per year between 2012 and 2015 (GLOBOCAN 2015) – locoregional therapies to address mCRC in the liver offer a potential route to local disease control in poor surgical candidates.

Transarterial chemoembolization (TACE), a treatment with proven efficacy against hepatocellular carcinoma, is one such option for patients with liver-dominant mCRC. TACE treatment consists of ‘loading’ HepaSphere Microspheres with a chemotherapeutic agent and delivering it to the target location by injection into the blood stream. In 2014, Huppert and colleagues published a case series of 29 mCRC patients who underwent 71 TACE procedures with irinotecan-loaded HepaSphere Microspheres® (Huppert 2014). All patients had previously undergone resection of their primary tumors, but were currently ineligible for resection of liver metastases that had progressed despite systemic chemotherapy. Each patient received one to three TACE treatments, with a mean interval of five weeks between TACE cycles.

Median survival and time to progression were 21 months and 10 months among patients with less than 25% liver volume involvement, 7 months and 4.5 months among patients with 26-50% liver volume involvement, and 5 months and 3 months among patients with 51-75% liver volume involvement, respectively. According to RECIST criteria, 12 of the 25 surviving patients (48%) had stable disease; by EASL criteria, four patients showed complete response, four showed partial response, and four had stable disease. At 12 months of follow-up, one patient of the 12 with follow-up imaging (8%) had stable disease and the remaining 11 had progressive disease. Toxicities associated with the TACE procedures included upper abdominal pain (severe in 32% of patients, moderate in 40% and mild in 28%) and nausea (ECOG 3 in 12%, ECOG 2 in 43% and ECOG 1 in 45%).

Similar studies have been conducted with DC Bead®. Aliberti et al. performed an initial cohort study in 10 patients with liver-dominant mCRC refractory to systemic chemotherapy who underwent TACE with irinotecan-loaded DC Bead (Aliberti 2006). At one month of follow-up, all patients demonstrated significant reduction in tumor contrast enhancement and carcinoembryonic antigen (CEA) reduction of at least 50%. Objective tumor regression was observed in seven patients. The same research group published serial expansions of their cohort, eventually enrolling 82 patients (Fiorentini 2007, Aliberti 2011). Patients underwent one to four TACE cycles, and all showed reduction in metastatic contrast enhancement. At 3 months of follow-up 78% of patients demonstrated response by RECIST criteria, with a median duration of response of six months. Median survival across the entire cohort was 24 months, with 8 months of progression-free survival.

A later phase III study randomized 74 patients with less than 50% hepatic parenchymal replacement and no extrahepatic spread to TACE with irinotecan-loaded DC Bead and systemic fluorouracil, leucovorin and

irinotecan (FOLFIRI) (Fiorentini 2012). At two years of follow-up, 56% of patients in the TACE group and 32% of those in the FOLFIRI group remained alive; survival dropped to 34% and 9% at 30 months, and 15% and 0% at 50 months among TACE and FOLFIRI patients, respectively. Progression-free survival was 7 months among TACE patients and 4 months among FOLFIRI patients ($p = 0.006$), but time to extrahepatic progression was not significantly different between the two groups. Objective response was observed in 68.6% of analyzed TACE patients and 20% of FOLFIRI patients. Severe neutropenia, diarrhea and mucositis were significantly more common among FOLFIRI patients, and liver enzyme and bilirubin elevations were significantly more common among TACE patients.

A U.S.-based cohort of 55 patients with liver-dominant mCRC who had received prior chemotherapy underwent TACE with irinotecan-loaded DC Beads and was followed for survival (Martin 2009). Adverse events were increasingly common with irinotecan dose escalation (50 mg to 200 mg). At 12 months of follow-up, 8 patients (15%) had complete response, 14 (25%) had partial response, 23 (42%) had stable disease and 10 (18%) had progressive disease according to mRECIST criteria (Martin 2011). Median overall survival for the cohort was 19 months, median progression-free survival was 11 months, and median hepatic-specific progression-free survival was 15 months.

Narayanan and colleagues have presented a retrospective analysis of 28 patients with hepatic metastases from CRC treated with irinotecan-loaded DC Bead (Narayanan 2013). These patients underwent one to five TACE procedures, and survived for a mean of 14.1 months. Complete response was observed in 3 (15%) patients, partial response was observed in 6 (30%), stable disease was observed in 4 (20%) and 7 patients (35%) showed progressive disease. The most common adverse events included nausea (47%), abdominal pain (43%), and vomiting (28%).

Only one publication to date has compared the efficacy of irinotecan-loaded HepaSphere Microspheres and DC Beads in the treatment of liver tumors (Namur 2015). In this study, performed in a VX2 rabbit model, treatment with irinotecan-loaded HepaSphere Microspheres resulted in significantly greater tumor necrosis and a significantly smaller area of residual tumor tissue than treatment with irinotecan-loaded DC Beads or bland HepaSphere Microspheres.

2.0 Study Objectives

Collectively, the studies above suggest that chemoembolization of metastatic colorectal cancer (mCRC) with irinotecan is a useful addition to the treatment armamentarium. HepaSphere Microspheres loaded with irinotecan received the CE mark for the indication of use in embolization of mCRC to the liver in 2015. Since that time, at least 100 patients with metastatic colorectal cancer to the liver have been treated with HepaSphere loaded with irinotecan within the context of this trial. The goal of this registry is to add to the understanding of the use and value of transarterial chemoembolization in 'real life' usage conditions.

2.1 Primary Objectives

- The primary study objective is the median overall survival of subjects treated with HepaSphere Microspheres loaded with irinotecan. Analysis will be performed when all subjects enrolled have been followed for survival for two years (24 months), are considered lost to follow up, or have died, whichever comes first. Survival time will be calculated in months and utilize the date of the first TACE procedure, the date of death (from any cause), and/or the last successful contact with the subject before they were considered lost to follow-up. Kaplan-Meier (product-limit) method will be used to assess median overall survival times.

2.2 Secondary Objectives

- Objective Response Rate (ORR) as determined by mRECIST criteria (Llovet 2008; Lencioni 2010). ORR will be calculated when all subjects enrolled have been followed for survival for two years (24 months from the date of their first TACE), are considered lost to follow up, or have died, whichever comes first
- Best Tumor Response (during the period of time between the first TACE and the last post TACE MRI or CT) as determined by mRECIST criteria
- Median liver progression-free survival will be calculated as the time (in months) between the first TACE procedure to the date on which progression of the subject's liver metastases was documented or the date of death (from any cause)
- Time to Progression, including extrahepatic progression, utilizing the date of the first study TACE as time zero

2.3 Additional Analyses

If sufficient data is available, additional exploratory analyses will also be conducted. These may include, but are not limited to:

- Pharmacokinetic (PK) Analyses: Plasma concentrations of irinotecan and SN38 will be analyzed at the following timepoints after the first TACE procedure: 30 minutes, 1 hour, 4 hours, 12 hours, and 24 hours or prior to discharge (whichever comes first).
- Additional TACE Cycles: The relationship between 'Additional TACE cycles,' (defined as cycles a subject may undergo after the protocol specified TACE 1 and TACE 2) and overall survival time (in months)
- RECIST 1.1: Reanalyze clinical outcomes using RECIST 1.1 criteria and compare best tumor response between RECIST 1.1 and mRECIST criteria.
- Clinical Success: Similar to ORR, clinical success will be based on the last post TACE liver response evaluated through mRECIST and RECIST 1.1 criteria. Clinical success is the total amount of confirmed subjects that have a complete or partial response [clinical success = (# CR + #PR)]

3.0 Study Design

This prospective, single arm, post-market clinical trial is designed to demonstrate safety and efficacy of Merit Medical Systems' HepaSphere Microspheres loaded with irinotecan for subjects with metastatic colorectal cancer to the liver. There will be two hospitals participating in this study, one in Greece and one in France. Hospitals and physicians with experience in routine use of chemoembolization for mCRC will participate. Subject recruitment and offer to participate in the study will be at the investigator's discretion (ensuring that subjects are existing patients receiving care at the hospital and that they meet inclusion and exclusion criteria).

4.0 Eligibility Criteria

4.1 Inclusion Criteria

The following inclusionary information must be evaluated by the investigator/institution to confirm the patient meets all of the following criteria:

- Histologically or radiologically confirmed colorectal cancer metastases to the liver
- Patient is able to have either CT or MRI imaging
- Hepatic tumor burden $\geq 50\%$ of total tumor burden
- Hepatic tumor burden $\leq 50\%$ of total liver volume
- Not suitable for treatment by resection or percutaneous ablation at time of TACE treatment
- Life expectancy ≥ 3 months
- WHO performance status ≤ 2

4.2 Exclusion Criteria

The following exclusionary information must be evaluated by the investigator/institution to confirm the patient does NOT meet any of the criteria below:

- Previous treatment with any form of hepatic transarterial embolization
- Total bilirubin ≥ 3.0 mg/dL
- Any contraindication for irinotecan administration
- Partial or complete thrombosis of the main portal vein
- Cardiovascular or respiratory failure
- Any other condition deemed exclusionary by the Investigator

4.3 Informed Consent

The subject must provide written informed consent prior to any study related procedures or interventions beginning. After the registry has been fully explained and the patient has had adequate time to thoroughly review the consent form, they will have the opportunity to have all their questions answered by their physician. Written informed consent will be obtained from either the patient or his/her guardian or legal representative prior to any registry procedures being performed. The patient will be given a copy of the consent form. The method of obtaining and documenting the informed consent and the contents of the consent will comply with ICH-GCP and all applicable regulatory requirement(s).

5.0 Study Procedures

5.1 Screening and Baseline Evaluation [within 4 weeks (28 days) of first TACE procedure]

- Assess subject eligibility
- Obtain Informed Consent
- Review and record relevant medical history, including demographics, WHO performance status, date of diagnosis of primary colorectal cancer and date of diagnosis of metastases to the liver, and prior systemic chemotherapy (with record of stop dates and number of cycles)
- Hematology and serum chemistry assessments, to include at a minimum:
 - Complete blood count
 - Aspartate aminotransferase (AST), alanine aminotransferase (ALT)
 - Total bilirubin
 - Serum albumin
 - Serum creatinine
- Computed tomography (CT) or contrast-enhanced magnetic resonance imaging (MRI) of the liver (note: the patient must receive the same form of imaging to evaluate disease response at follow up visits)
- Positron emission tomography (PET) imaging, or equivalent, to assess extrahepatic metastases

5.2 Transarterial chemoembolization (TACE) procedure(s)

- Each patient must have at least 2 TACE cycles (Lencioni 2014). A TACE cycle is defined as one embolization for patients with unilobar disease or two embolizations for subjects with bilobar disease (one for each lobe of the liver)
 - Note: It is at the investigator's discretion to evaluate the number and size of lesions and determine if embolization of both lobes (bilobar) can occur in a single embolization session or if both lobes should be embolized separately
- The first TACE procedure must be within 4 weeks of the baseline imaging date

- If bilobar disease is treated with two embolizations in a TACE cycle (one per lobe), the second lobe must be embolized within 3 weeks of the first lobe
- The second TACE cycle should be performed within 2-4 weeks after the first TACE cycle
- The maximum Irinotecan dosage per TACE procedure is 100mg (200mg per TACE cycle)
- Liver enzymes should be observed to ensure they return to acceptable levels before performing the next embolization
- Subsequent TACE cycles may be performed for residual or new disease as needed (at the investigators discretion), based on tumor response
- Embolizations may be performed using the 30-60 μ m or 50-100 μ m size HepaSphere Microspheres. Embolic size is determined by the Investigator based on their judgment of tumor size and vascularity
- Pharmacokinetic (PK) Blood samples will be drawn on a portion of subjects following their first TACE procedure at the following time points: 30 minutes, 1 hour, 4 hours, 12 hours, and 24 hours or prior to discharge (whichever comes first)
- Periprocedural Medications and Supportive Treatment
- Investigator will follow institutional standards of care and irinotecan manufacturer's Instructions for Use regarding periprocedural medications and supportive treatment, including:
 - Hydration regimens, sedation protocols, pain management, nausea and emesis prevention, prophylactic antibiotic treatment, and gastric and pancreatic protection

5.3 Follow-Up Schedule

- Patients should return for follow-up 4-6 weeks (28-42 days) post the second TACE cycle, then every 12 weeks (\pm 2 weeks) thereafter. Follow up may be more frequent if medically indicated
- Additional TACE procedures can be performed for residual or new disease as needed at the discretion of the physician; however, liver enzymes should be at acceptable levels before performing additional TACE cycles
- The liver should remain the dominant site of metastases for additional TACE cycles to be performed
- Each follow-up visit will include, at a minimum:
 - CT or MRI of the liver (the method of follow-up imaging should be consistent with baseline imaging)
 - PET or similar imaging to assess presence and/or progression of extrahepatic disease
 - Objective tumor response rate as determined by mRECIST criteria
 - Hematology and serum chemistry assessments as at baseline
 - Review of adverse events, including unscheduled hospitalizations
 - Review of any additional treatments performed outside of this registry for metastatic disease

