5.4 Survival follow-up

If a subject is no longer indicated for TACE, they will enter survival follow-up. During survival follow-up, subjects are contacted every three months (\pm 2 weeks) to determine their survival status. Subjects can be contacted (via phone, email, written response), their medical records reviewed, and/or information can be obtained from additional sources (i.e., the subject's caregivers/family members) to determine if the subject is alive. These survival contacts should continue until one of the following conditions is met:

- Subject dies
- Subject withdraws consent

- Subject is classified as lost to follow-up

Lost to follow-up (LTFU): All reasonable efforts will be made to obtain complete data for all subjects. Missing observations from unsuccessful contact attempts will occur due to some subjects being LTFU, having withdrawn from the study, or not adhering to required assessments. Three (3) total attempts shall be made to contact a subject. If a subject cannot be accounted for (i.e., by visit, telephone call, email, written response, family member report, etc.) and has not followed-up accordingly with the clinical site, they will be considered lost to follow-up. Study data collected on this subject, up to the date and time of loss to follow-up (or subject withdrawal) will remain in the study database and used for analysis purposes, as appropriate. These subjects will not be replaced. Survival follow-up information will be collected within the electronic database capture (EDC) system.

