APPENDIX A

Schedule of Procedures

	Screening ¹	TACE Procedure ²	Follow Up Visits ³	Survival Follow-up ⁴
Informed Consent	X			
Eligibility criteria assessment	X			
Demographics	X			
Medical History	X			
Tumor Evaluation / Imaging	X		X	
Hematology / Serum Chemistry	X			
Embolization procedures (TACE)		X		
Pharmacokinetic Sampling ⁵		X		
Additional cancer treatments			X	
Adverse Events		X	X	
Survival status				X

¹ Screening imaging must be within 4 weeks of first TACE cycle.

² First TACE cycle must be within 4 weeks of screening imaging. If the patient has bilobar disease, the embolization of the first lobe must be within 4 weeks of screening imaging and the second lobe must undergo embolization within 3 weeks (\pm 2 weeks) of the first lobe. A second TACE cycle is required for all patients 2-4 weeks after the first TACE cycle. Additional TACE cycles can be performed for residual or new disease as needed.

³ Follow up Visits will start 4-6 weeks after the second TACE cycle and occur every 12 weeks (\pm 2 weeks) thereafter during the first year of follow-up. Follow-up may be more frequent if medically indicated.

⁴ If patients are no longer indicated for TACE, they will continue to be followed for survival for 2 years after the first TACE procedure, with contacts performed every 3 months (\pm 2 weeks).

⁵ Blood samples will be drawn for PK analysis from a portion of study patients after the first TACE procedure at the following time points; 30 min, 1 hour, 4 hours, 12 hours, and 24 hours or prior to discharge (whichever comes first).

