2.3. STUDY POPULATION

Subjects (meeting inclusion/exclusion criteria and having signed informed consent) will be included in the study analysis if they have had at least one protocol specified TACE procedure.

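### All post-treatment clinic visits are timed from the second TACE cycle, so a treated patient who does not receive that cycle has no scheduled tumor assessment

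*Protocol*

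**What the plan says.** Protocol 5.3 sets the clinic follow-up: "Patients should return for follow-up 4-6 weeks (28-42 days) post the second TACE cycle, then every 12 weeks". Each such visit includes liver CT or MRI, PET or similar imaging, blood tests, and review of adverse events and of other treatments. Footnote 3 of Appendix A, repeated in SAP 2.6, keeps the anchor: "Follow up Visits will start 4-6 weeks after the second TACE cycle". The only flexibility is that "Follow up may be more frequent if medically indicated".

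The second cycle is presented as mandatory: "Each patient must have at least 2 TACE cycles" (Protocol 5.2). The analysis populations do not require it. Under SAP 2.3, eligible and consented subjects "will be included in the study analysis if they have had at least one protocol specified TACE procedure". The safety set (Protocol 7.0, SAP 3.2) also needs only one TACE. The efficacy set (Protocol 7.0, SAP 3.1) needs one TACE plus a tumor evaluation after baseline.

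Protocol 5.4 covers patients who stop: "If a subject is no longer indicated for TACE, they will enter survival follow-up". In the schedule table, the survival follow-up column is marked for survival status and nothing else.

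**The concern.** The documents foresee patients who stop after one cycle. Protocol 5.2 makes the next embolization depend on liver enzymes, Protocol 8.0 lets the investigator withdraw a patient for adverse events or progression, and every analysis set admits a patient with a single TACE. For such a patient the event that starts the visit clock never happens. A site that follows the text exactly has no date on which to scan.

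It is reasonable to expect that patients who stop after one cycle do worse than those who go on, although the documents give no data on this. If so, the missing assessments are informative. The ORR, best response, liver PFS and TTP results would then describe mainly patients who were able to have two cycles, while the stated population is everyone with at least one TACE.

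**Working it through.** **1. Where a tumor assessment is scheduled.** The schedule table marks tumor evaluation at screening and at follow-up visits only. It marks adverse events at the TACE procedure and at follow-up visits. It marks survival status in survival follow-up only.

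**2. When the first follow-up visit falls.** Protocol 5.2: "The second TACE cycle should be performed within 2-4 weeks after the first TACE cycle". Adding the visit window of 4-6 weeks gives 2 + 4 = 6 to 4 + 6 = 10 weeks after the first cycle. This ignores the extra time for two-session bilobar cycles. Without a second cycle, the date is undefined in Protocol 5.3 and in both footnotes.

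**3. What the analysis rules then do if no scan is recorded.**
- ORR and best response: the patient fails the SAP 3.1 requirement. SAP 5.1 imputes nothing and bases percentages on non-missing values. The patient leaves the denominator and is not counted as a non-responder.
- Liver PFS and TTP: under the efficacy population the patient is excluded. If all treated patients are used, as SAP 2.3 suggests, liver progression is never seen. Liver PFS can then end only at death or at the last date known alive, which biases it long, and TTP has no progression date.
- Safety: the patient stays in, because one TACE is enough.

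**4. The plan's own counts.** Treated patients: 100 + 5 = 105 by site (SAP 2.1), 76 + 29 = 105 by cycle group (Table 7 shell), and N = 105 in the safety shell (Table 3). These agree.
- mRECIST shells (Tables 5 and 6): N = 83; 105 - 83 = 22; 22/105 = 21.0% missing.
- RECIST 1.1 shells: N = 78; 105 - 78 = 27; 27/105 = 25.7% missing.

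No planned table counts patients with only one cycle. The Table 7 groups are standard and additional cycles, and 76 + 29 already accounts for everyone, so one-cycle patients must sit inside the standard group.

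**5. Possible effect on ORR.** Let *u* be the number of the 22 who are unscanned one-cycle patients. Restoring them as non-responders multiplies ORR by 83/(83 + *u*):
- *u* = 0: 1.000
- *u* = 11: 83/94 = 0.883
- *u* = 22: 83/105 = 0.790

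The documents do not locate *u* within 0 to 22. The last factor is also the effect of counting all the unassessed as non-responders, whatever the cause. With assumed responder counts (no results are given):

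| Responders (assumed) | Over 83 | Over 105 |
|---|---|---|
| 25 | 30.1% | 23.8% |
| 42 | 50.6% | 40.0% |
| 57 | 68.7% | 54.3% |

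**6. Another explanation for the 22.** Early death also prevents a scan. Assume exponential survival with medians quoted in Protocol 1.0 from earlier studies. Ten weeks is 10 × 7 × 12/365.25 = 2.30 months, and expected deaths by then are 105 × (1 - 2^(-2.30/median)):
- median 24 months: 6.7
- median 21 months: 7.7
- median 7 months: 21.4

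Early deaths and one-cycle patients may overlap. The shell counts therefore cannot be read as a count of one-cycle patients.

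**The case against.** Several points on the other side are sound and limit the claim.

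- **Safety.** A reader might infer that one-cycle patients drop out of the safety data. They do not. The safety shell holds all 105, adverse events are marked at the procedure itself, related events must be reported and followed to resolution (Protocol 6.0), and related serious events must reach the sponsor within 24 hours of the site learning of them (6.3). None of this depends on a second cycle. What remains is weaker: with no scheduled review, late non-serious events and laboratory changes may be under-ascertained.
- **Survival.** A reader might infer that all follow-up hangs on the second cycle. Survival contacts do not: in Appendix A, "they will continue to be followed for survival for 2 years after the first TACE procedure".
- **Response.** Exclusion is a risk and not a certainty. The efficacy set accepts any post-baseline tumor evaluation, ORR uses the last recorded post-TACE scan, and data are abstracted from standard-of-care records (Protocol 9.0). A patient who stops because a scan showed progression is evaluable if that scan is recorded. Permission to follow more often does not guarantee a scan, though, and whether one exists would depend on clinical judgment.
- **Route.** Delayed enzyme recovery does not by itself end TACE, and patients withdrawn under 8.0 may not be reachable by a new visit.
- **Deviations.** Stopping after one cycle departs from the plan, and deviations will be summarized. That would record the departure but would not supply the missing assessment.
- **Timing.** Protocol 2.0 says at least 100 patients have already been treated, so a new visit anchor can change little for them. This is correct and shapes the fix.

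**Conclusion.** The gap is real. The plan admits patients with one TACE but schedules tumor assessment only for those who reach the second cycle. Unless some other scan is recorded, a one-cycle patient leaves ORR and best response, and is excluded from liver PFS and TTP or kept there with progression unseen. The direction is towards a favourable result, on the assumption that patients who stop early do worse.

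The size is unknown. It is tempting to read the 22 missing mRECIST responses (21.0%) as one-cycle patients. The documents do not support this: no reason is given for any of them, and death, loss to follow-up, missed visits or unreadable scans are all possible. Nor does 22 cap the number of one-cycle patients, since some may have been scanned. The factor 0.790 is the outer limit for ORR, and it assumes that the shell denominators equal the patients with an evaluable response.

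A related inconsistency needs settling. Protocol 7.1 calls overall survival the primary efficacy analysis, so read literally the scan requirement reaches it, whereas SAP 2.3 and the Table 7 shell point to all treated patients. The point should be corrected, but it does not by itself invalidate the study.

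**What to change.** 1. In Protocol 5.3 and in footnote 3 of Appendix A and of SAP 2.6, add a fallback assessment visit for any treated patient without a second cycle, timed from the last embolization performed and held before transfer to survival follow-up. This also covers a bilobar patient who stops after one lobe. It sets an assessment date and changes no treatment rule.
2. For patients already treated, retrieve existing standard-of-care liver scans and related adverse events from medical records. With at least 100 already treated, this step and step 4 must carry most of the correction.
3. Report how many patients received only one cycle, why, and how many of them had a post-baseline scan.
4. Report ORR also with all treated patients as denominator, counting the unassessed as non-responders.
5. Reconcile the two-cycle requirement in Protocol 5.2 with the populations that need one TACE, and SAP 2.3 with SAP 3.1. State which set is used for overall survival, liver PFS and TTP.

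The cost is a wording amendment, one added table line, and some record abstraction (for mRECIST response, at most the 22 patients not in the shell). No new type of procedure is added. Reported ORR and PFS may become slightly less favourable.
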